### List of Key Terms

Terms	Definition of terms
Baseline	The last non-missing measurement prior to initial dosing of study drug(Screening or Day1)
Study period	Period of time from the time point when written informed consent is obtained from the subject and the end of the final assessment/observation specified in the protocol.
Treatment period	Period of time from the first study drug administration for the treatment period to the end of Week 52 visit or the end of the withdrawal visit in case of withdrawal.
Follow-up period	The follow-up period will be 4 weeks (on a per-protocol basis) starting after the early-termination visit for withdrawn subjects and after the Week 52 visit for subjects who completed the study but are not willing to enroll into the extension study. For subjects who completed the study and wish to enroll into the extension study, the follow-up period will last for a maximum of 4 weeks starting after the Week 52 visit and ending at the initiation of the extension study treatment.
Subject	An individual who participates in a clinical trial as a recipient of the study drug.
Week 12/ET	Week 12 or early termination before Week 12
Week 28/ET	Week 28 or early termination before Week 28
EOT	Week 52 or early termination before Week 52

Discontinuation	When a subject who was enrolled in the study discontinues his/her participation in the study before the completion of all the protocol-specified items of the study.
Variable	Any quantity that varies; any attribute, phenomenon or event that can have different qualitative or quantitative values.

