  - The mean-standard deviation plot of actual values and changes from baseline will be presented for DAS28-CRP and DAS28-ESR.

<mTSS, Erosion Score, and Joint Space Narrowing Score>

In this analysis, mTSS, Erosion Score, and Joint Space Narrowing Score will be imputed using linear extrapolations as described in the primary analysis.

- Categorical variables at each visit (including Week 28/ET, Week 52/ET) will be analyzed using Fisher's exact test.
  - mTSS change from baseline  $\geq 3$
  - mTSS change from baseline  $\leq 0.5$
  - mTSS change from baseline  $\leq 0$
- Yearly progression of mTSS will be analyzed
- Percentage of subjects showing Rapid Radiographic Progression: RRP (Yearly progression of mTSS  $\geq 5$ )
- Raw value and change from baseline variables at each visit (including Week 28/ET, EOT) will be analyzed using the RANCOVA model with treatment group (Placebo, ASP015K 100 mg, ASP015K 150 mg) as factor and baseline rank mTSS as covariate.
  - mTSS (Week 52/ET)
  - Erosion Score (Week 28/ET, Week 52/ET)
  - Joint Space Narrowing Score (Week 28/ET, Week 52/ET)
- Graphical analysis (including Week 28/ET, Week 52/ET).
  - Cumulative probability plot for the change from baseline in mTSS score, Erosion Score, Joint Space Narrowing Score will be presented at Week 28/ET, Week 52/ET.
  - Scatter plot for mTSS score at baseline to mTSS at Week 28/ET, Week 52/ET will be presented.
  - Scatter plot for mTSS score at baseline to mTSS change from baseline at Week 28/ET, Week 52/ET will be presented.

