#### **7.11.4 Handling of Schedule of Assessments of Efficacy Variables**

For data after the end of study treatment, data obtained within +2 days after the last dose is taken will be included in analysis. Baseline for efficacy is defined as value at Day 1 before the first dose of study drug for all subjects including placebo assigned subjects. For Week

12/ET, or Week 28/ET, the values at closest date to reference date will be used. As for the subjects who switched to receive ASP015K instead of placebo at Week 12, the last observation before first dose of ASP015K at Week 12 will be used for the analysis for visit Week 4, 8, 12, 12/ET. In addition, the subjects who switched to receive ASP015K instead of placebo at Week 28, the last observation before the first dose of ASP015K at Week 28 will be used for the analysis for visit Week 4, 8, 12, 12/ET, 28/ET. For EOT, the closest value to the reference date will be used regardless of the switching from placebo.

(1) TJC (68 joints)/SJC (66 joints), laboratory test (CRP)

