**Table6. Visit Window for Hand and foot radiography**

Time points defined in analysis	Reference date*	Acceptable time range
Baseline	Day 1	Day 1 to Day 30
Week 28	Day 197	Day 160 to Day 234
Week 52	Day 365	Day 328 to Day 402
Week 28/ET (Week 28 or at early termination before Week 28)	Day 197	Day 48 to Day 234
EOT (Week 52 or at early termination)	Day 365	Day 48 to Day 402

\*: Day 1 represents the first day of study treatment. The day before is expressed as Day -1.

- (3) PGA and SGA (VAS), subject's assessment of pain (VAS), HAQ-DI, laboratory test (ESR)

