5.1	Percentage of subjects achieving "Good Response" or "Moderate Response" using DAS28 EULAR response criterion at each visit (Baseline, Week 4, 8, 12, 12/ET,28/ET)	X	X		Placebo, 100mg, 150mg	Fisher's exact test.
5.2	Percentage of subjects achieving "Good Response" or "Moderate Response" using DAS28 EULAR response criterion at each visit (Baseline, Weeks 4, 8, 12, 16, 20, 24, 28, 32, 36, 40, 44, 48, 52, EOT)	X	X		100mg, 150mg	No statistical test.
6.1	Percentage of subjects in ACR/EULAR remission at each visit (Baseline, Week 4, 8, 12, 12/ET,28/ET)	X			Placebo, 100mg, 150mg	Fisher's exact test.
6.2	Percentage of subjects in ACR/EULAR remission at each visit (Baseline, Weeks 4, 8, 12, 16, 20, 24, 28, 32, 36, 40, 44, 48, 52, EOT)	X			100mg, 150mg	No statistical test.
7.1	Percentage of subjects in SDAI <= 3.3 at each visit (Baseline, Week 4, 8, 12, 12/ET,28/ET)	X			Placebo, 100mg, 150mg	Fisher's exact test.
7.2	Percentage of subjects in SDAI <= 3.3 at each visit (Baseline, Weeks 4, 8, 12, 16, 20, 24, 28, 32, 36, 40, 44, 48, 52, EOT)	X			100mg, 150mg	No statistical test.

8.1	Percentage of subjects in CDAI $\leq$ 2.8 at each visit (Baseline, Week 4, 8, 12, 12/ET,28/ET)	X			Placebo, 100mg, 150mg	Fisher's exact test.
8.2	Percentage of subjects in CDAI $\leq$ 2.8 at each visit (Baseline, Weeks 4, 8, 12, 16, 20, 24, 28, 32, 36, 40, 44, 48, 52, EOT)	X			100mg, 150mg	No statistical test.
9.1	Percentage of subjects achieving HAQ-DI ( $\leq$ 0.5) at each visit (Baseline, Week 4, 8, 12, 12/ET,28/ET)			X	Placebo, 100mg, 150mg	Fisher's exact test.
9.2	Percentage of subjects achieving HAQ-DI ( $\leq$ 0.5) at each visit (Baseline, Weeks 4, 8, 12, 16, 20, 24, 28, 32, 36, 40, 44, 48, 52, EOT)			X	100mg, 150mg	No statistical test.
9.3	Percentage of subjects achieving decrease of baseline HAQ-DI of at least 0.22 at each visit (Baseline, Week 4, 8, 12, 12/ET,28/ET)			X	Placebo, 100mg, 150mg	Fisher's exact test.
9.4	Percentage of subjects achieving decrease of baseline HAQ-DI of at least 0.22 at each visit (Baseline, Weeks 4, 8, 12, 16, 20, 24, 28, 32, 36, 40, 44, 48, 52, EOT)			X	100mg, 150mg	No statistical test.
10.1	Percentage of subjects showing no progression of joint damage (mTSS change from baseline $\leq$ 0.5) at each visit (Baseline, Week 28/ET, EOT)			X	Placebo, 100mg, 150mg	Fisher's exact test.

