10.2	Percentage of subjects showing no progression of joint damage (mTSS change from baseline $\leq$ 0) at each visit (Baseline, Week 28/ET, EOT)			X	Placebo, 100mg, 150mg	Fisher's exact test.
10.3	Percentage of subjects showing Clinically Relevant Radiographic Progression: CRRP (mTSS change from baseline $\geq$ 3) at each analysis visit			X	Placebo, 100mg, 150mg	Fisher's exact test.
10.4	Percentage of subjects showing Rapid Radiographic Progression: RRP (Yearly progression of mTSS $\geq$ 5)			X	Placebo, 100mg, 150mg	Fisher's exact test.

11.1	Percentage of subjects achieving SF-36v2 of difference $\geq 5$ at each visit (Weeks 4, 8, 12, 12/ET, 28/ET)	X			Placebo, 100mg, 150mg	Fisher's exact test.
11.2	Percentage of subjects achieving SF-36v2 of difference $\geq 5$ at each visit (Weeks 4, 8, 12, 28, 52, EOT)	X			100mg, 150mg	No statistical test.
Continuous Variables						
12.1.1	Raw value and change from baseline in mTSS score at each visit (Baseline, Week 52/ET)			X	Placebo, 100mg, 150mg	Descriptive Statistics RANCOVA  analysis with Week 52/ET. No multiplicity adjustment.
12.1.2	Raw value and change from baseline in Erosion Score at each visit (Baseline, Week 28/ET, Week 52/ET)			X	Placebo, 100mg, 150mg	Descriptive Statistics; RANCOVA  analysis with each visit. No multiplicity adjustment.
12.1.3	Raw value and change from baseline in Joint Space Narrowing Score at each visit (Baseline, Week 28/ET, Week 52/ET)			X	Placebo, 100mg, 150mg	Descriptive Statistics; RANCOVA  analysis with each visit. No multiplicity adjustment.
12.2.1	Cumulative probability plot for the change from baseline in mTSS score at Week 52/ET			X	Placebo, 100mg, 150mg	
12.2.2	Cumulative probability plot for the change from baseline in Erosion Score at Week 28/ET, Week 52/ET			X	Placebo, 100mg, 150mg	
12.2.3	Cumulative probability plot for the change from baseline in Joint Space Narrowing Score at Week 28/ET, Week 52/ET			X	Placebo, 100mg, 150mg	
12.3.1	Scatter plot for mTSS score at baseline to Week 28/ET, Week 52/ET			X	Placebo, 100mg, 150mg	
12.3.2	Scatter plot for mTSS score at baseline to mTSS change from baseline at Week 28/ET, Week 52/ET			X	Placebo, 100mg, 150mg	
12.4.1	Yearly Progression of mTSS			X	Placebo, 100mg, 150mg	Descriptive Statistics;
13.1.1	Raw value and change from baseline in DAS28	X	X		Placebo, 100mg, 150mg	Descriptive Statistics;

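### Appendix 2 puts the no-progression tests against placebo at EOT, whose written rule takes in post-switch films, while the SAP text puts them at Week 52/ET, which excludes them

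*SAP*

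**What the plan says.** **Appendix 2 (SAP 10.2).** Items 10.1 and 10.2 list the groups Placebo, 100 mg and 150 mg, name Fisher's exact test, and set the time points "at each visit (Baseline, Week 28/ET, EOT"). Item 10.3 (change of 3 or more) has the same groups and test but names no time point.

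**Text on the same variables.** The radiographic part of SAP 7.4.2 states: "Categorical variables at each visit (including Week 28/ET, Week 52/ET) will be analyzed". It then lists the cut-offs of 3, 0.5 and 0. It opens by saying that the scores "will be imputed using linear extrapolations as described in the primary analysis". SAP 7.1 also puts mTSS tests against placebo at Week 28/ET and Week 52/ET.

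**Rule for EOT.** The key terms define EOT as "Week 52 or early termination before Week 52". SAP 7.11.4 adds: "For EOT, the closest value to the reference date will be used regardless of the switching from placebo". Table 6 gives radiographs an EOT row with reference Day 365 and a window of Day 48 to Day 402. It has no Week 52/ET row.

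**Rule for Week 52/ET.** Under SAP 7.11.1, a placebo subject's value is extrapolated linearly to Day 365 from baseline and the early-termination film or the last film before switching. Observed Week 52 films are used only for subjects randomised to an active arm.

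**Switching.** Under SAP 3.2, inadequate responders on placebo switch at Week 12 and everyone still on placebo switches at Week 28.

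**The concern.** The overview table and the text assign one set of tests to two time points with different data rules. A programmer working from Appendix 2 finds a complete EOT rule for radiographs in 7.11.4 and Table 6, and can run it without ever meeting the Week 52/ET rule. The output would carry a placebo column and a p-value, yet most of the placebo values would come from patients on ASP015K.

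At stake is how the one-year structural result is read. If the drug works, the placebo no-progression rate would be improved by the drug itself and the difference pulled toward zero. Because both readings can be programmed, the choice should be settled in writing before unblinding.

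**Working it through.** **Step 1. Which label goes with which test.**

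| Place in SAP | Variable | One-year time point |
|---|---|---|
| Appendix 2, items 10.1 and 10.2 | change ≤ 0.5, ≤ 0; Fisher | EOT |
| Appendix 2, item 10.3 | change ≥ 3; Fisher | not named |
| 7.4.2, categorical bullet | change ≥ 3, ≤ 0.5, ≤ 0; Fisher | Week 52/ET |
| 7.1 | mTSS tests against placebo | Week 52/ET |
| 7.4.2, RANCOVA bullet, lead line | raw value and change | EOT |
| 7.4.2, RANCOVA sub-bullets | mTSS, erosion, narrowing | Week 52/ET |
| Appendix 2, items 12.1.1 to 12.1.3 | mTSS, erosion, narrowing; RANCOVA | Week 52/ET |

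The other Appendix 2 rows that name EOT show active arms only, or treatment sequences, with no test against placebo. Items 10.1 and 10.2 are the only rows that pair EOT with a Placebo column and a test.

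**Step 2. One placebo subject under each rule.** Take a placebo subject with a Week 52 film.
- EOT uses that film. Time on ASP015K is 52 − 28 = 24 weeks (24/52 = 46% of the year) after a Week 28 switch, or 52 − 12 = 40 weeks (40/52 = 77%) after a Week 12 switch.
- Week 52/ET ignores that film and extrapolates the pre-switch change to Day 365. The multiplier is 364/196 = 1.86 from a Week 28 film and 364/84 = 4.33 from a Week 12 film.

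**Step 3. Planning inputs.** The documents give no figure for the Week 52 tests. SAP section 4 gives an mTSS change at Week 28 of 2.0 (placebo) and 0.5 (150 mg), SD 4.0, two-sided 5%, 90% power and 151 per group. A two-sample t-test with difference 1.5 and SD 4.0 needs 150.4, rounded up to 151; power at 151 is 90.1%. The inputs therefore reproduce the plan's sample size.

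**Step 4. Illustration on mean change.** Assume linear progression at those rates and an immediate full 150 mg effect after switching.
- 150 mg at Week 52: 0.5 × 52/28 = 0.93.
- Placebo under Week 52/ET: 2.0 × 52/28 = 3.71. Difference 3.71 − 0.93 = 2.79 (unrounded 2.786).
- Placebo under EOT, Week 28 switch: 2.0 + 0.5 × 24/28 = 2.43. Difference 1.50, which is 46% lower (1 − 1.50/2.786).
- Placebo under EOT, Week 12 switch: 2.0 × 12/28 + 0.5 × 40/28 = 0.86 + 0.71 = 1.57. Difference 0.64, which is 77% lower (1 − 0.643/2.786).

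With a share f switching at Week 12, the EOT difference is 1.50 − 0.857f. The documents do not give f, so the full range 0.64 to 1.50 stands.

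**Step 5. What this does not give.** Items 10.1 and 10.2 test proportions. Turning mean changes into proportions at or below 0.5 or 0 needs the distribution of mTSS change, which the documents do not provide. They also give no planning rate for 100 mg.

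**The case against.** The strongest reply is that EOT is only a loose label for Week 52/ET. The specific radiographic text in 7.1, 7.4.2 and 7.11.1 consistently keeps post-switch films out of the placebo arm, and Appendix 2 is an overview. This probably describes the intent. It does not remove the problem: the key terms define EOT but not Week 52/ET, the radiograph window table has only an EOT row, and 7.11.4 states in terms that EOT ignores switching. Nothing says which text prevails.

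Three stronger readings are tempting, and the documents do not support them.
- *A reader might infer that the RANCOVA results are equally exposed*, because the lead line says "Raw value and change from baseline variables at each visit (including Week 28/ET, EOT) will be analyzed using the RANCOVA model". The sub-bullets beneath it and items 12.1.1 to 12.1.3 all name Week 52/ET. Only the lead line is wrong.
- *A reader might carry the drop in mean difference over to the no-progression tests.* The illustration concerns a different summary of the data, and the mean-change analysis is itself assigned to Week 52/ET.
- *A reader might take Week 52/ET to be a true one-year placebo comparison.* No subject is on placebo after Week 28, so every placebo value at that time point is extrapolated, by a factor of about 4.3 for Week 12 switchers.

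It is also fair to say that the consequence is limited. SAP 7.4.2 applies no multiplicity adjustment to secondary variables, and the error would work against the drug.

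**Conclusion.** The inconsistency is real and confined to the one-year no-progression analyses. Followed literally, items 10.1 and 10.2 compare the active arms with a placebo arm made up mostly of switched patients; item 10.3 leaves the same choice open. The direction, dilution of the difference, holds provided the drug slows progression.

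On mean change the illustrative loss is 46% to 77% of a 2.79 difference. That rests on linear progression, the planning rates, an immediate full 150 mg effect and an unknown share switching at Week 12. The size of the effect on the tested proportions is not known. The primary mTSS test at Week 28/ET is unaffected, and so are the sample size and the testing sequence.

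**What to change.** 1. Replace EOT by Week 52/ET in Appendix 2 items 10.1 and 10.2.
2. Name Week 28/ET and Week 52/ET in item 10.3.
3. Change EOT to Week 52/ET in the lead line of the RANCOVA bullet in 7.4.2, to match its sub-bullets.
4. Add a Week 52/ET row to Table 6 that points to the extrapolation rule in 7.11.1.
5. State in 7.11.4 that the EOT rule does not apply to placebo comparisons of radiographic scores.

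The cost is wording in five places, with no new data, no new output and no change to the sample size. The downside is that the placebo values at Week 52/ET are all extrapolated. That is already the SAP's stated rule, and the report should say so beside these results. If the wording cannot be settled before unblinding, the clinical study report should justify which rule was used.

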### 10.3 Appendix 3: Overview of AE analysis

Table16, Table17 summarizes the analyses of AE occurrence, the analysis of SOC, PT analysis, with "X1", "X2", "X3", and "X4" indicating that the variable will be analyzed by each defined groups defined footnote. All analyses will be based on the SAF.

**Table16. The overview of AE occurrence analysis**

	Overall	Week 0 to Week 12	Week 12 to Week 28	Week 28 to Week 52
Number and percentage of subjects with TEAE	X4	X1	X2	X3
Number and percentage of subjects with drug related TEAE	X4	X1	X2	X3
Number and percentage of subjects with death	X4	X1	X2	X3
Number and percentage of subjects with serious TEAE	X4	X1	X2	X3
Number and percentage of subjects with drug related serious TEAE	X4	X1	X2	X3
Number and percentage of subjects with TEAE Grade 3 or Higher in Severity	X4	X1	X2	X3
Number and percentage of subjects with TEAE leading to study drug discontinuation	X4	X1	X2	X3
Number and percentage of subjects with drug related TEAE leading to study drug discontinuation	X4	X1	X2	X3
Number and percentage of subjects with Serious TEAE Leading to Permanent Discontinuation of Study Drug	X4	X1	X2	X3
Number and percentage of subjects with Drug-Related Serious TEAE Leading to Permanent Discontinuation of Study Drug	X4	X1	X2	X3

X1: Placebo, 100mg, 150mg

X2: Placebo, 100mg, 150mg, Placebo to 100 mg at Week 12, Placebo to 150 mg at Week12

X3: 100mg, 150mg, Placebo to 100 mg at Week 12, Placebo to 150 mg at Week 12, Placebo to 100 mg at Week 28, Placebo to 150 mg at Week 28

X4: 100mg, 150mg

**Table17. The overview of the number of SOC/PT analysis**

	Overall	Week 0 to Week 12	Week 12 to Week 28	Week 28 to Week 52
TEAEs	X4	X1	X2	X3

Drug related TEAEs, defined as any TEAE with possible, probable or missing relationship to study drug as assessed by the investigator.	X4	X1	X2	X3
Serious TEAEs	X4	X1	X2	X3
Drug related serious TEAEs		X1		
TEAEs by severity based on NCI-CTCAE	X4	X1	X2	X3
Drug related TEAEs by severity		X1		
Grade 3 or higher TEAEs by severity	X4	X1		
TEAEs by relationship to study drug		X1		
TEAEs leading to death	X4	X1	X2	X3
TEAEs leading to permanent discontinuation of study drug	X4	X1	X2	X3
Drug related TEAEs leading to permanent discontinuation of study drug		X1		
Serious TEAEs leading to permanent discontinuation of study drug		X1		
Drug related serious TEAEs leading to permanent discontinuation of study drug		X1		
TEAEs excluding serious adverse events that equal to or Exceed a threshold of 5% in Any Treatment Group	X4			
Most common TEAEs (> 5% in any treatment group)	X4	X1	X2	X3
Most common serious TEAEs (> 5% in any treatment group)	X4	X1	X2	X3
TEAEs by subgroups defined in section 7.8.		X1		
The number and percentage of subjects with TEAEs of special interest	X4	X1		
Serious Infections	X4	X1		
Malignancies	X4	X1		
Herpes Zoster Related Disease (Herpes Zoster and Varicella)	X4	X1		
Herpes Zoster	X4	X1		
Varicella	X4	X1		
Infections That Require Intravenous Anti-infectious Therapy	X4	X1		
Subgroup				
Sex		X1		
Age Group		X1		
Prior Anti-TNF DMARD Use		X1		
Prior Biologic DMARD Use		X1		
Duration of RA (years)		X1		

Number of Prior DMARDs Used		X1		
Number of Prior Biologic DMARDs Used		X1		
MTX Dose (mg/week) at Baseline (0 <- 8 mg/week, 8 <- 12 mg/week, >12 mg/week)		X1		
Concomitant Steroid at Baseline (No, Yes)		X1		
Prednisone Dose at Baseline (mg/day) (None, 0 <- 5 mg/day, > 5 mg/day)		X1		
Body Weight (kg) at Screening		X1		

X1: Placebo, 100mg, 150mg

X2: Placebo, 100mg, 150mg, Placebo to 100 mg at Week 12, Placebo to 150 mg at Week12

X3: 100mg, 150mg, Placebo to 100 mg at Week 12, Placebo to 150 mg at Week 12, Placebo to 100 mg at Week 28, Placebo to 150 mg at Week 28

X4: 100mg, 150mg

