2 STUDY OBJECTIVE(S), DESIGN, AND VARIABLES

2.1 Study Objectives

The main objective of this study is to evaluate the efficacy of ASP015K (100 and 150 mg/day) versus placebo administered in combination with MTX in RA patients who had an inadequate response to MTX. The primary efficacy variables are the ACR20 response rate at Week 12 and suppression of joint destruction (change from baseline in mTSS) at Week 28. This study will also investigate pharmacokinetic, pharmacodynamic, and safety profiles. Furthermore, this study will examine the long-term efficacy and safety (52 weeks).

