## 4 SAMPLE SIZE

A total of 510 treated patients, with 170 in each treatment group

[Rationale for the sample size]

The sample size calculation was based on ASP015K Japanese Phase IIb study (015K-CL-RAJ1) result and other Japanese studies for patients with RA [XELJANZ®, tablet, 5 mg, CTD (2013)] [CIMZIA, sc, 200 mg, Syringe, CTD (2012)]. In the 015K-CL-RAJ1 study, the primary efficacy endpoint, which was Percentage of Subjects achieving ACR20 response at Week 12/ET, was 54.5% in the 100 mg, and 65.5% in the 150 mg. Therefore, in the 015K-CL-RAJ4 study, it can be assumed to achieve same magnitude of ACR20 response at Week 12/ET for both 100 mg and 150 mg. For ACR20 response at Week 12/ET in the placebo group, it was assumed 25% based on other Japanese drugs for RA.

Meanwhile, the change in mTSS at Week 28 was estimated to be 0.5 in ASP015K 150 mg group, considering the results of the Japanese subgroup analysis of the Oral Scan Study of Tofacitinib, a drug of same class and indication (5 mg group: -0.0, 10 mg group: 0.5), Study CDP870-041 of Cimzia (100 mg group: 1.05, 200 mg group: 0.21, 400 mg group: 0.65), and Study RA0006 (200 mg group: 0.44). Similarly, the change in mTSS at Week 28 was estimated to be 2.0 in the placebo group, considering the results of the Japanese subgroup analysis of the Oral Scan Study (placebo group: 1.4), Study CDP870-041 (placebo group: 2.78), and Study RA0006 (placebo group: 2.49). The standard deviation of the change was also estimated and set to 4.0 based on the results reported from the same studies [Japanese subgroup analysis of the Oral Scan Study (placebo group: 3.15, 5 mg group: 1.09, 10 mg

group: 1.54), Study CDP870-041 (placebo group: 5.15, 100 mg group: 2.85, 200 mg group: 2.01, 400 mg group: 2.95), and Study RA0006 (placebo group: 5.52, 200 mg group: 1.83)].

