On this assumption, the necessary sample size was calculated to enable to analyze ACR20 using the Fisher's exact test and the change in mTSS at Week 28 using the t-test. When a closed testing procedure (in Section 7.4.1.1 Primary Analysis) considering multiplicity is used in the primary analysis, the sample size needed to verify the hypotheses Step 1 through Step 3 at a 2-sided 5% significance level with 90% power is 151 subjects per group. By considering about 10% drop-out, this study will enroll 170 patients in each treatment group. Moreover, from the long term safety point of view, this sample size is also needed to keep 300 subjects for 6 month period, 100 subjects for 1 year period in both ASP015K 100 mg and 150 mg among RAJ2/RAJ3/RAJ4 studies.

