SEQ2	150mg	ASP015K 150 mg	ASP015K 150 mg	ASP015K 150 mg	
SEQ3	Placebo to 100mg at Week 12	Placebo	ASP015K 100 mg	ASP015K 100 mg	
SEQ4	Placebo to 150mg at Week 12	Placebo	ASP015K 150 mg	ASP015K 150 mg	
SEQ5	Placebo to 100mg at Week 28	Placebo	Placebo	ASP015K 100 mg	
SEQ6	Placebo to 150mg at Week 28	Placebo	Placebo	ASP015K 150 mg	

- 100 mg: subjects who initially treated ASP015K 100 mg
- 150 mg: subjects who initially treated ASP015K 150 mg

- Placebo to 100 mg at Week 12: subjects who initially treated Placebo group and switched 100 mg at Week 12 and at least one dose of ASP015K 100 mg drug after switched
  - Placebo to 150 mg at Week 12: subjects who initially treated Placebo group and switched ASP015K 150 mg at Week 12 and at least one dose of ASP015K 150 mg drug after switched
  - Placebo to 100 mg at Week 28: subjects who initially treated Placebo group and switched ASP015K 100 mg at Week 28 and at least one dose of ASP015K 100 mg drug after switched
  - Placebo to 150 mg at Week 28: subjects who initially treated Placebo group and switched ASP015K 150 mg at Week 28 and at least one dose of ASP015K 150 mg drug after switched
- 
- The analyses for mTSS (Appendix 1, Appendix 2), erosion score, and joint space narrowing score will be performed at Week 28/ET and Week 52/ET, and statistical testing will also be conducted at Week 28/ET, Week 52/ET, compared with Placebo. These analyses include primary analysis (mTSS change from baseline at Week 28/ET).
  - MedDRA 11.1 will be used as the coding dictionary for adverse event and medical history.
  - Statistical hypothesis testing will be performed only if specified. All statistical comparisons of treatment groups will be versus placebo (i.e., each ASP015K treatment versus placebo) and will be made using two sided tests at the 0.05 significance level, unless stated otherwise. Multiplicity adjustment will be done in the primary analysis and other analysis if specified.
  - Statistical analysis including hypothesis testing for efficacy variables to compare 100 mg or 150 mg versus Placebo, only the data for the pairwise comparison will be used.
  - All statistical results will be presented, as appropriate, by treatment group, by treatment group and scheduled visit; the schedule of assessments is provided in 7.11.4.

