#### Definition 2:

TEAEs per 100 PYs =  $100 \times (\text{Number of TEAEs for all subjects in the treatment group} / \text{Total PYs in the treatment group})$ .

For number of TEAEs for all subjects in the treatment group, multiple occurrences of the same TEAE in the same subject will be counted multiple times.

Total PYs will be calculated by summing subjects' durations in study through the follow-up period. Each subject's duration will be calculated as:  $(\text{last date of follow-up in the study} - \text{date of initial dose of study drug} + 1) / 365.25$ .

Patient-Year analysis will be calculated by Placebo, 100 mg, 150 mg, 100mg+150mg, ASP015K Total, Total.

The number of TEAEs and AEs per 100 PYs will be provided by Definition 2, for all TEAEs (if analyzable), by SOC and PT for each treatment group, ASP015K Total and Total.

Patient-Year analysis for following specified AE will also be conducted by Definition 1 with 95% confidence interval.

- Serious Infections
- Malignancies
- Herpes Zoster Related Disease (Herpes Zoster and Varicella)
- Herpes Zoster
- Varicella
- Infections That Require Intravenous Anti-infectious Therapy

Note: Definition will be provided in the Appendix 8.

Confidence Interval for TEAEs per 100 patient-years will be calculated for AE of special Interest based on following formula (assuming Poisson distribution).

- Upper limit of CI (TEAEs per 100 PYs) :  $100 * \exp\left(\log\left(\frac{A}{T}\right) + Z_{\alpha} * \sqrt{\frac{1}{A}}\right)$
- Lower limit of CI (TEAEs per 100 PYs) :  $100 * \exp\left(\log\left(\frac{A}{T}\right) - Z_{\alpha} * \sqrt{\frac{1}{A}}\right)$

A: Number of subjects who had at least 1 incidence

T: Total PYs by 100 PYs as one unit

$Z_{(\alpha)}$ : alpha % point of standard normal distribution

alpha = 0.025

In addition, the subgroup analysis of Sex, Age Group, Concomitant Steroid at Baseline, and Predonisone Dose at Baseline will be conducted.

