### Patient-year analysis

	Week 0 to Week 12	Overall Period
TEAEs	X1	X4
TEAEs of special interest	X1	X4
Serious Infections	X1	X4
Malignancies	X1	X4
Herpes Zoster Related Disease (Herpes Zoster and Varicella)	X1	X4
Herpes Zoster	X1	X4
Varicella	X1	X4
Infections That Require Intravenous Anti-infectious Therapy*	X1	X4
Subgroup		
Sex		X4
Age Group		X4
Concomitant Steroid at Baseline (No, Yes)		X4
Prednisone Dose at Baseline (mg/day) (None, 0 <- 5 mg/day, > 5 mg/day)		X4

X1: Placebo, 100mg 150mg

X4: 100mg 150mg

\*: subgroup analysis will not be conducted.

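### On-drug adverse events of special interest (AESI) in switched placebo patients enter no AESI count table, and the SAP contradicts itself on whether and how they enter the AESI rates

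*SAP*

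**What the plan says.** **Counts.** SAP 10.3 Appendix 3 assigns comparison groups by code. In Table 17 the row "The number and percentage of subjects with TEAEs of special interest" and the six rows beneath it (serious infections, malignancies, zoster-related disease, herpes zoster, varicella, infections needing intravenous therapy) carry X1 for Week 0-12 and X4 for Overall. Their Week 12-28 and Week 28-52 cells are empty. X1 is placebo, 100 mg and 150 mg. X2 and X3 are the codes that include the placebo-to-ASP015K groups. X4 is 100 mg and 150 mg only. The rows for all TEAEs, serious TEAEs, fatal TEAEs and TEAEs leading to discontinuation carry all four codes.

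SAP 7.1 defines the dose labels: "100 mg: subjects who initially treated ASP015K 100 mg", with a matching line for 150 mg. SAP 7.5 assigns adverse-event analysis after Week 12 to the Treatment Sequence Set, which contains the four switch groups, and refers to Appendix 3 for details. SAP 6.2 attributes events with onset after the switch to ASP015K.

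**Rates.** SAP 7.5.1.2 states: "Patient-Year analysis will be calculated by Placebo, 100 mg, 150 mg, 100mg+150mg, ASP015K Total, Total". It plans the six AESI under Definition 1 with a 95% confidence interval. The patient-year table in Appendix 3 has only a Week 0-12 column (X1) and an overall column, footnoted "X4: 100mg 150mg". SAP 7.5 says these analyses use Groups for Patient-Years, a set that is defined nowhere. Both rate definitions count time from the initial dose.

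**The concern.** Every placebo patient still on study at Week 28 has moved to ASP015K by then, and stays on it for up to 40 weeks (Week 12 switch) or 24 weeks (Week 28 switch). Protocol 1.4 asks investigators to pay particular attention to infections and malignancies, and Protocol 2.1 makes 52-week safety an objective. AESI are rare, so on-drug follow-up matters for their counts and intervals. Under Appendix 3 as written, this follow-up contributes to no AESI count, although SAP 6.2 and 7.5 treat the events as ASP015K events to be analysed by treatment sequence.

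The rates have a second problem. If switchers are brought in through ASP015K Total with the clock as defined, 12 or 28 weeks of placebo time per patient enters an on-drug denominator.

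**Working it through.** The documents give no exposure figure for this point. The arm size comes from SAP section 4: "A total of 510 treated patients, with 170 in each treatment group". That size is consistent with its own basis. A two-sided 5% t-test for a difference of 2.0 - 0.5 = 1.5 with SD 4.0 has power 0.899 at 150 per group and 0.901 at 151, and 151/0.9 gives 168, enrolled as 170.

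**Inputs.** 340 patients on ASP015K from Day 1 for 52 weeks; 170 on placebo. Let f be the fraction of placebo patients who switch at Week 12 (40 weeks on drug); the rest switch at Week 28 (24 weeks on drug). The documents do not give f. The assumed 25% placebo ACR20 rate does not fix it, because the switch rule uses joint counts only.

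**1. Share of on-drug exposure from switchers, no dropout.**
170(24 + 16f) / [340 × 52 + 170(24 + 16f)] = (24 + 16f) / (128 + 16f)

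- f = 0: 24/128 = 18.75% (78.2 patient-years)
- f = 0.3: 51 × 280/365.25 + 119 × 168/365.25 = 93.8 patient-years; 93.8/432.6 = 21.7%
- f = 0.6: 102 × 280/365.25 + 68 × 168/365.25 = 109.5 patient-years; 109.5/448.3 = 24.4%
- f = 1: 40/144 = 27.8% (130.3 patient-years)

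The randomised active arms supply 340 × 364/365.25 = 338.8 patient-years. The share passes 20% when f exceeds 12.5%.

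**2. With dropout.** Equal exponential dropout of 10% by Week 52 gives 18.3% to 27.5% (20% is passed at f = 17%). Dropout of 10% by Week 28 gives 17.9% to 27.3% (20% is passed at f = 20%). With heavier placebo loss before the switch (17.9% or 25% assumed, none on active), the share is 16.8% to 22.1% for f from 0.25 to 0.75.

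**3. Effect on interval width.** The SAP interval has log-scale half-width proportional to 1/√A, where A is the number of patients with an event. At a constant rate, leaving out 21.7% or 24.4% of exposure widens it by √(1/0.783) = 1.13 or √(1/0.756) = 1.15, that is 13-15%.

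**4. Effect of starting the clock at the initial dose.** If switchers are included from Day 1, the denominator is 510 × 364/365.25 = 508.3 patient-years instead of 432.6 (f = 0.3) or 448.3 (f = 0.6). With on-drug events only in the numerator, the understatement is 1 - 432.6/508.3 = 14.9% or 1 - 448.3/508.3 = 11.8%. In general it is (28 - 16f)/156, from 17.9% at f = 0 to 7.7% at f = 1. This ignores the follow-up period and the small loss of time after a first event.

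**The case against.** A reader might infer that these events reach no AESI table of any kind, that the 52-week safety objective loses over a fifth of its exposure, and that a malignancy or zoster signal could go unreported. The documents do not support that.

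- **Rates.** ASP015K Total stands beside 100mg+150mg in SAP 7.5.1.2, which is redundant unless it adds switchers. SAP 7.1 describes it as all ASP015K groups combined and presents safety by actual treatment. SAP 7.5.1 also suggests rates by period. The initially-treated label belongs to the Treatment Sequence Set, which 7.1 introduces for efficacy, whereas patient-years use a different, undefined set. For rates this is a conflict, not a proven omission.
- **Other tables.** Serious TEAEs carry X2 and X3 in the same Table 17. Serious infections are defined in SAP Appendix 8 as serious events in the infections system organ class, so that count is a row of that table. Protocol Appendix 3 makes malignant tumours always serious. Zoster and varicella terms appear in the all-TEAE table, and all events are listed.
- **Size.** More than a fifth is not certain, because it depends on f. No switcher has 52 weeks on drug, and the randomised arms supply the full 52-week data.
- **Intent.** SAP 7.1 calls the switch-group analyses optional.

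All of this stands. It does not fill the AESI count cells. Infections needing intravenous therapy depend on linked medication (SAP Appendix 8) and cannot be read from term tables. Malignancies and zoster are multi-term groups, so unique-patient counts cannot be obtained by adding term rows. ASP015K Total is also mentioned for counts in SAP 7.5.1.1, but SAP 7.5 defers to Appendix 3 for the groups, and the Overall column there holds only the two initially treated arms.

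**Conclusion.** The point holds in limited form. For counts, the gap is clear from Table 17 and conflicts with SAP 6.2 and 7.5. For rates, SAP 7.5.1.2 and Appendix 3 disagree, the group set is undefined, and the starting date is wrong for switchers on any reading that includes them.

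What is lost is the grouped AESI counts for switched patients and, on the Appendix 3 reading, their contribution to AESI rates and intervals. The events themselves are not hidden. The on-drug time concerned is 18.75-27.8% of the planned total without dropout (22-24% if 30-60% switch at Week 12, an assumption). The 12-15% understatement of the rate rests on the same assumption, 170 placebo patients and no dropout, and arises only if switchers are included with the clock as written. The change should be made; it does not touch the primary analysis.

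**What to change.** 1. In Table 17, put X2 in the Week 12-28 cell and X3 in the Week 28-52 cell of every AESI row.
2. Define Groups for Patient-Years and ASP015K Total, and make SAP 7.5.1, 7.5.1.2 and the Appendix 3 patient-year table agree on groups and periods. That table has no Week 12-28 or Week 28-52 columns, so the simplest change is an All ASP015K overall column, by dose and combined, that includes switchers. Add the same overall column to the AESI rows of Table 17.
3. For switchers in that column, count only events with onset on or after the first ASP015K dose, and start person-time at that dose under both rate definitions.
4. Keep X4 as the randomised-arm display.

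The cost is SAP wording and a few extra tables, with no new data. The pooled column mixes randomised and switched exposure, so it should be shown beside X4.
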